## **6.2 Biopsy of metastatic lesion**

After signing informed consent for the research biopsy, potential participants should have a biopsy of a metastatic lesion as per Section 11 below. Tissue from the metastatic biopsy needs to be available, but not required to have been evaluated centrally, prior to beginning treatment on study.

Outside sites should ship specimens along with the Tissue Registration Form (located in the lab manual) directly to:

### **For all tissue and blood/plasma:**

**Ship ALL paraffin material, RNAlater tubes or slides as detailed in the lab manual.  
\*\*Specimens should be mailed to arrive at VUMC from Monday 8AM through Friday 1PM\*\***

## 7. STUDY CALENDARS

### 7.1 STUDY CALENDAR: CARBOPLATIN +/- ATEZOLIZUMAB

Procedure		Screening Day -28 to Day 1 b	Cycle 1 (21-days) Day 1 a,b	Additional cycles a Day 1	End-of-treatment d	30 day (+/- 3 days) follow-up d	1, 2 & 3 year follow-up n
Informed consent		X					
Inclusion/exclusion criteria		X					
Demographics/ medical history (SOC)		X					
Physical exam/signs/symptoms e (SOC)		X	X	X	X		
Vital signs (including oxygen sat) c (SOC)		X	X	X	X		
Single 12-lead ECG		X					
ECOG Performance Status (SOC)		X	X	X	X		
Blood collection	Clinical laboratory tests f (SOC)	X	X	X	X		
	Serum pregnancy test (SOC) f	X					
	TSH, free T3, T4 g (After screening, atezolizumab arm only)	X		X (every 4 th cycle)	X		
	PT (or INR) and PTT	X					
	HIV, HBV, HCV serology h	X					
	Circulating tumor DNA		X	X (Cycle 2 only)	X		
	Mononuclear Cell Collection		X	X (Cycle 2 only)	X		
Tumor assessment CTs, bone scan i (SOC)		X		X (every 3 cycles)			
Archived tumor blocks/slides j		X					
Tumor biopsy (metastatic site) k		X			X		
Carboplatin administration (IV) (SOC)			X	X l			
Atezolizumab administration (IV): if on atezolizumab arm			X	X			
Concomitant medications m		X	X	X			
Adverse events		X	X	X		X	X n
Biopsy questionnaire o				X (cycle 2, day 1)			
BRCA 1 and 2 testing p (SOC)		X					

**AE** = adverse event; **BSA** = body surface area; **CX** = Cycle X, where X is the cycle number; **DLT** = dose-limiting toxicity; **ECG** = electrocardiogram; **ECOG** = Eastern Cooperative Oncology Group; **HbA1C** = glycosylated hemoglobin; **IMP** = investigational medicinal product; **INR** = international normalized ratio; **PT** = prothrombin time; **PTT** = partial prothrombin time; **SAE** = serious adverse event **SOC** = Standard of Care; all tests not indicated as SOC are research-related.

- a Evaluation assessments should be performed prior to administration of IMP unless otherwise indicated. Results should be reviewed by the Investigator prior to the administration of the next dose. **All visits must occur within  $\pm$  3 days from the scheduled date unless otherwise noted.** Delays up to 7 days will be considered by Study Chair.
- b Screening must occur within 28 days of dosing. The following procedures must be repeated at the day 1 visit if they were previously done  $>7$  days prior to study treatment administration: Medical and cancer history, physical examination, weight measurement, vital signs, hematology, serum chemistry panel. Tumor assessments must be repeated at the baseline visit only if determined to be changed by clinical exam or other clinical observations. SOC procedures performed prior to consent but within the protocol defined screening window for each assessment can be used for study purposes. All research only procedures must be performed after the consent date.
- c See section 10.1.2 for vital sign information during atezolizumab infusion.
- d The 30-day follow-up assessments should be done 30 ( $\pm$ 3 days) days after the last dose of study drugs. 30 day follow-up can be done by phone or by a clinic visit. Any ongoing toxicities should be documented. Any ongoing serious adverse events will be followed every 3 months (in person or by phone) until resolution. Any AEs or SAEs considered possibly or probably related to IMP that have not stabilized, returned to baseline, or are considered irreversible will continue to be monitored as per the protocol.
- e The physical examination will include measurements of height and weight at screening. Weight will be measured on day 1 of each cycle and at the End-of-treatment visit. Dosing changes are only required if the weight changes 10% or more. Physical examination will include examination of major body systems including neurologic, cardiac, respiratory, gastrointestinal, and skin. Clinically relevant signs and symptoms will be reported as AEs.
- f Clinical laboratory tests will include hematology and serum chemistry panel including white blood cell count, differential, hemoglobin, platelet count, sodium, potassium, chloride, bicarbonate, BUN, creatinine, glucose, calcium, and magnesium, AST (SGOT), ALT (SGPT), and total serum bilirubin, albumin, and total protein. Additional tests will be performed when clinically appropriate. In case of Grade 3 or higher AST/ALT, additional testing will be done weekly until recovery to baseline value (see protocol section 9.1.2 and 9.2.2.1). Labs do not have to be repeated on cycle 1, day 1 if they were done up to 7 days prior to day 1. For all other timepoints, labs can be performed up to 3 days prior to each timepoint indicated in the study calendar. **Results from labs obtained on CID1 (up to -7 days) must meet eligibility criteria. At the start of each cycle, the ANC must be  $\geq 1000/\text{mm}^3$  and the platelet count must be  $\geq 80,000/\text{mm}^3$  (see section 9.2.1) for carboplatin to be administered. Atezolizumab may be administered if these criteria are not met at the discretion of the treating physician. Serum pregnancy test does not need to be performed for patients  $\geq 55$  years old, those who are known to be post-menopausal, or who have had a hysterectomy.**
- g Thyroid function studies: see section 9.1.4 for abnormal results
- h All patients will be tested for HIV and HIV-positive patients will be excluded from the clinical trial. Please note that this result must be back by the time patient starts study so it is advised this be drawn prior to day 1 if the result may take some time to obtain. HBV serology includes Hepatitis B surface antigen, anti-HBc, and anti-HBs. As above, it is advised the HBV serology be obtained in advance if results may be delayed. Hepatitis B virus (HBV) DNA must be collected on or before Cycle 1, Day 1 in patients who have negative serology for hepatitis B surface antigen and positive serology for anti-HBc.
- i Tumor assessment should be performed approximately every 3 cycles (up to -5 days) while on study treatment (i.e. on or up to 5 days prior to Day 1 of Cycles 4, 7, 10 etc) and at End-of-treatment visit if not obtained within the past 6 weeks. Scans should consist of CT scan of the chest, abdomen, and pelvis and a bone scan at baseline. Of note, if the prior bone scan did not show metastases, it does not need to be repeated if the bone scan was obtained within 8 weeks of CID1. Subsequent scans should consist of CT chest, abdomen and pelvis, and bone scan if bone metastases were present on the baseline studies. MRI is also an acceptable form of imaging. At the end of treatment, all scans (baseline and through disease progression) should be sent on a CD to the Vanderbilt Cancer Imaging Support Laboratory for central review and assessment. See Section 12.6 for details and address.
- j Archived tumor biopsy specimen: Archived biopsy block (unstained slides) will be requested at the time of registration prior to initiation of treatment. See Section 11.1 for details. If archived tissue is not available, the VICC coordinating center should be contacted.
- k After signing consent, a fresh tumor biopsy from a metastatic site amenable to a reasonably safe biopsy will be obtained prior to day 1 and upon progression of disease (see Section 11). The second biopsy will not be required for patients who are removed from study for reasons other than disease progression. A patient who undergoes a research biopsy procedure for the purpose of this protocol, in whom inadequate tissue is obtained, is not obligated to undergo a repeat biopsy.

- l After cycle 6, at the discretion of the treating physician, carboplatin can be stopped and atezolizumab can be continued as a single agent.
- m The dose of steroids before each carboplatin injection should be recorded. Prohibited medications (section 8) must be discontinued at least 7 days prior to initiation of study drug (C1D1).
- n 1, 2, and 3 year follow-up can be done by phone or chart review to document survival status, and if applicable, the date of death and cause of death. Surveillance for Adverse Events of Special Interest (AESIs) (see section 13.5.12) should be included.
- o Biopsy questionnaire should be filled out by the patient on C2D1. Form can be found in the packet of supplemental forms.  
BRCA 1/2 testing and results are not required prior to enrollment. However, all patients in whom BRCA status is unknown must be referred for testing during the screening period. Testing must be sent for analysis prior to C3D1, although results need not be available. This is a standard procedure as per NCCN guidelines. The VICC coordinating center should be contacted if a patient's insurance will not pay for testing and an exception may be granted.

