## 7.2 STUDY CALENDAR: ATEZOLIZUMAB (CROSSOVER)

Crossover therapy (atezolizumab) must begin no later than 21 days after the clinic visit at which progression is determined.

Procedure	Cycle 1 a (21-days)	Additional cycles a	End-of-treatment c	30 day follow-up b	1, 2, 3 year follow-up i
	Day 1	Day 1			
Physical exam/signs and symptoms c	X	X	X		
Vital signs (including oxygen sat)	X	X	X		
ECOG Performance Status	X	X	X		
Blood collection	Clinical laboratory tests d	X	X		
	TSH, free T3, T4 e	X		X (every 4 th cycle)	
	Circulating tumor DNA	X	X (Cycle 2 only)	X	
	Mononuclear Cell Collection	X	X (Cycle 2 only)	X	
Tumor assessment CTs, bone scan f		X (every 3 cycles)			
Tumor biopsy (metastatic site) at crossover g	X				
Atezolizumab administration (IV)	X	X			
Concomitant medications h	X	X			
Adverse events	X	X		X	X i

- Evaluation assessments should be performed prior to administration of IMP unless otherwise indicated. Results should be reviewed by the Investigator prior to the administration of the next dose. All visits should occur within 3 days of scheduled visit unless otherwise noted. Delays up to 7 days will be considered by study chair. Crossover therapy (atezolizumab) must begin no later than 21 days after the clinic visit at which progression is determined. Exceptions must be discussed with the Protocol Chair.
- The 30-day follow-up assessments should be done 30 (±3 days) days after the last dose of study drugs. 30 day follow-up can be done by phone or by a clinic visit. Any ongoing toxicities should be documented. Any ongoing serious adverse events will be followed every 3 months until resolution. Any AEs or SAEs considered possibly or probably related to IMP that have not stabilized, returned to baseline, or are considered irreversible will continue to be monitored as per the protocol.
- The physical examination will include measurements of height and weight at screening. Weight will be measured on day 1 of each cycle and at the End-of-treatment visit. Physical examination will include examination of major body systems including neurologic, cardiac, respiratory, gastrointestinal, and skin. Clinically relevant signs and symptoms will be reported as AEs.

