### 8.4 Cross-over post-progression

Patients who are randomized to carboplatin alone can cross over to receive atezolizumab upon disease progression based on clinical progression or radiographic progression. Patients who are randomized to carboplatin alone and who discontinue carboplatin for toxicity cannot cross over to receive single agent atezolizumab. There may be exceptions to this based on discussion with the Protocol Chair. However, patients on the carboplatin + atezolizumab arm can continue to receive single agent atezolizumab if they discontinue carboplatin due to toxicity. Patients who cross over to receive atezolizumab will follow the assessments and procedures as outlined in the study calendar. The duration of each cycle will continue to be 21

days and the cycle numbers will "reset" to 1 and will be followed by the "X" suffix (e.g., Cycles 1X, 2X, etc.). Crossover therapy (atezolizumab) must begin no later than 21 days after the clinic visit at which progression is determined.

Patients must have labs and procedures performed as outlined in the cross-over study calendar and must meet the values as described in the Inclusion Criteria, prior to receiving atezolizumab based on assessments and procedures performed within 21 days prior to Day 1 of Cycle 1X. Labs and procedures not included in the cross-over study calendar do not have to be repeated. Patients must also agree to a tumor biopsy, as outlined in the eligibility criteria, prior to initiating atezolizumab. Patients will receive crossover treatment until progression, intolerable toxicity, or elective withdrawal from the study. Patients who cross over will be evaluated with radiologic assessments every 3 cycles until disease progression.

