#### Management Guidelines for Endocrine Events

Event	Management
Asymptomatic hypothyroidism	
 
• Continue atezolizumab.
 
• Initiate treatment with thyroid replacement hormone.
 
• Monitor TSH weekly.
 

Symptomatic hypothyroidism	
 
• Withhold atezolizumab.
 
• Initiate treatment with thyroid replacement hormone.
 
• Monitor TSH weekly.
 
• Consider patient referral to endocrinologist.
 
• Resume atezolizumab when symptoms are controlled and thyroid function is improving.
 

Asymptomatic hyperthyroidism	
TSH <math>\geq</math> 0.1 mU/L and <math><</math> 0.5 mU/L:
 
 
• Continue atezolizumab.
 
• Monitor TSH every 4 weeks.
 
 
TSH <math><</math> 0.1 mU/L:
 
 
• Follow guidelines for symptomatic hyperthyroidism.
 

Symptomatic hyperthyroidism	
 
• Withhold atezolizumab.
 
• Initiate treatment with anti-thyroid drug such as methimazole or carbimazole as needed.
 
• Consider patient referral to endocrinologist.
 
• Resume atezolizumab when symptoms are controlled and thyroid function is improving.
 
• Permanently discontinue atezolizumab and contact Study Chair for life-threatening immune-related hyperthyroidism.c
 

MRI=magnetic resonance imaging; TSH = thyroid-stimulating hormone.

Note: Management guidelines are presented by adverse event severity based on NCI CTCAE and are applicable to both CTCAE Version 4.0 and CTCAE Version 5.0

a Atezolizumab may be withheld for a longer period of time (i.e.,  $>$ 12 weeks after event onset) to allow for corticosteroids (if initiated) to be reduced to the equivalent of  $\leq$  10 mg/day oral prednisone. The acceptable length of the extended period of time must be agreed upon by the

investigator and the Study Chair.

- b If corticosteroids have been initiated, they must be tapered over  $\geq 1$  month to the equivalent of  $\leq 10$  mg/day oral prednisone before atezolizumab can be resumed.

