### 13.3 Safety Parameters and Definitions

#### 13.3.1 Adverse Event (AE)

An AE is any unfavorable and unintended sign, symptom, or disease temporally associated with the use of an investigational medicinal product (IMP) or other protocol-imposed intervention, regardless of attribution.

This includes the following:

- AEs not previously observed in the patient that emerge during the protocol-specified AE reporting period, including signs or symptoms that were not present prior to the AE reporting period
- Complications that occur as a result of protocol-mandated interventions (e.g., invasive procedures such as cardiac catheterizations)
- If applicable, AEs that occur prior to assignment of study treatment associated with medication washout, no treatment run-in, or other protocol-mandated intervention
- Pre-existing medical conditions (other than the condition being studied) judged by the investigator to have worsened in severity or frequency or changed in character during the protocol-specified AE reporting period
- Abnormal laboratory values or diagnostic test results constitute adverse events only if they induce clinical signs or symptoms or require treatment or further diagnostic tests.

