## 17.4 Statistical Analysis Plan

Demographic information, such as age and race, will be tabulated. Descriptive statistics, including means, standard deviations, and ranges for continuous parameters, as well as percents and frequencies for categorical parameters, will be presented. Investigation for outliers and assumptions for statistical analysis, e.g., normality and homoscedasticity, will be made. If necessary, data will be

transformed by utilizing appropriate transformations such as log or square root. Adverse medical events will be tabulated. NCI toxicity Grade 3 and Grade 4, and laboratory abnormalities will be listed.

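### Thyroid tests after screening are scheduled only on atezolizumab, so part of any thyroid adverse-event difference between arms or periods would reflect the testing schedule

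*Combined protocol and SAP*

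**What the plan says.** **Randomised period.** In Section 7.1 the row for TSH, free T3 and T4 applies to everyone at screening. It then carries the restriction "After screening, atezolizumab arm only", with draws every fourth cycle and at end of treatment.

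**Crossover period.** The Section 7.2 calendar has its own thyroid row. Its columns are displaced in the text available to me; I read it as crossover Cycle 1 and then every fourth cycle. The first footnote to that calendar says "Evaluation assessments should be performed prior to administration of IMP unless otherwise indicated", so the Cycle 1 sample comes before atezolizumab. Section 8.4 makes the calendar binding: "Patients who cross over to receive atezolizumab will follow the assessments and procedures as outlined in the study calendar".

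**When a laboratory finding counts.** Under Section 13.3.1, abnormal results "constitute adverse events only if they induce clinical signs or symptoms or require treatment or further diagnostic tests".

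**What follows a finding.** For hypothyroidism without symptoms, the endocrine table in Section 9.2.4 says "Initiate treatment with thyroid replacement hormone" and adds weekly TSH. For mild asymptomatic hyperthyroidism it calls for TSH every four weeks.

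**Analysis.** Section 17.4 says "Adverse medical events will be tabulated" and that laboratory abnormalities will be listed. It has no rule for events whose detection depends on a test scheduled in one arm only.

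**The concern.** A scheduled thyroid test can itself create a recorded adverse event. If it shows asymptomatic hypothyroidism, the endocrine table calls for treatment and repeat testing, and either one meets the Section 13.3.1 definition. The same abnormality in a control patient on carboplatin who has no symptoms and no test leaves no record. Two patterns could then appear in the safety table: more thyroid events on the combination than on carboplatin, and a rise in control patients when they cross over. Both would mix any real atezolizumab effect with the difference in testing.

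This matters because Section 8.1 describes the trial as evaluating the safety profile of carboplatin with or without atezolizumab. Section 4.1.1.2.2 lists hypothyroidism as a common atezolizumab risk (1% to 10%), and Section 13.5.11 makes hyperthyroidism an event of special interest. Readers will look at thyroid rates by arm.

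**Working it through.** The plan gives no thyroid rate or comparison, so there is no figure of its own to reproduce. The check has three parts.

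**1. How unequal is the scheduled testing?**

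Inputs: 53 patients per arm and median PFS of 4.4 months on the combination (Section 17.2), 21-day cycles (Section 8.1), and thyroid draws every fourth cycle and at end of treatment (Section 7.1). Assumptions: exponential PFS, treatment lasting as long as PFS, every patient having the end-of-treatment draw, and 30.4375 days per month.

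- Probability of still being on treatment at time t months: S(t) = exp(−ln 2 × t / 4.4).
- Every fourth cycle could mean a first draw at Cycle 4 (63 days, 2.07 months) or Cycle 5 (84 days, 2.76 months). S = 0.722 or 0.647.
- Later draws are 84 days apart, so each is reached with 0.647 times the previous probability. Expected on-treatment draws are 0.722 / (1 − 0.647) ≈ 2.0 or 0.647 / (1 − 0.647) ≈ 1.8 per patient.
- Adding one end-of-treatment draw gives, from unrounded values, 53 × 3.047 ≈ 162 or 53 × 2.836 ≈ 150 scheduled draws in the combination arm.
- Control arm, after screening and before crossover: 0 by the calendar. Control patients who never cross over have no further scheduled thyroid test at all.

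**2. What difference could this produce on its own?**

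Let p be the true rate of new asymptomatic thyroid abnormality, taken as equal in the two arms. Let s be the share found in controls by clinically prompted tests. Assume all are found on atezolizumab. The recorded rates are then p and p × s, and the spurious difference is p − p × s = p(1 − s).

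The documents give neither p nor s. The range of p below borrows the 1% to 10% frequency band for hypothyroidism on atezolizumab as a scale only; it is not a carboplatin rate.

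| p | Expected in 53 combination patients | Expected in 53 controls, s = 0 to 0.5 | Spurious difference, s = 0.5 to 0 |
|---|---|---|---|
| 1% | 0.53 | 0 to 0.27 | 0.5 to 1.0 points |
| 5% | 2.65 | 0 to 1.33 | 2.5 to 5.0 points |
| 10% | 5.3 | 0 to 2.65 | 5.0 to 10.0 points |

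If s = 1 or p = 0, the difference is zero. Incomplete detection on atezolizumab would shrink it.

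**3. What happens at crossover?**

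Section 13.1 collects adverse events from the first study medication. A thyroid abnormality that arises on carboplatin without symptoms would have its first scheduled chance of detection in the crossover Cycle 1 sample. That sample is taken before atezolizumab, so the abnormality belongs to carboplatin time. Section 17.4 does not say which period it is counted in.

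**The case against.** The strongest reply is that no stated analysis is wrong. Section 17.4 promises a tabulation, with no test and no explicit split by arm or period, and Section 3 has no safety objective. Closer monitoring for a known risk of one drug is a reasonable choice, and the calendar states it openly. This stands as far as it goes: the comparison is implied by randomisation and crossover, not written down. It does not remove the point, because a two-arm safety table will be read across its columns.

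Other parts of the reply limit the claim:

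- A reader might infer that control patients cannot have a thyroid test or event before crossover. The documents do not support that. Footnote f in Section 7.1 allows further tests when clinically indicated, and signs and symptoms are reviewed each cycle in both arms. What is missing is scheduled testing. The specific advice to test thyroid function for unexplained symptoms does, however, sit in the atezolizumab toxicity section (9.2.4).
- A reader might take the background prevalence of thyroid abnormality as the size of the bias. Both arms are tested at screening, and Section 13.5.4 counts a pre-existing condition only if it worsens. The relevant rate is that of new abnormality over a few months.
- A reader might infer that crossover findings will be blamed on atezolizumab. Section 13.4 requires start dates, and its causality guidance asks for a plausible time relation to dosing. Correct use of these would prevent wrong attribution. They do not settle which period the event is tabulated in.
- Comparing arms on symptomatic events alone may look like a clean solution, but it is not. The trial is open-label, and early treatment after a scheduled test may stop some atezolizumab patients from ever developing symptoms.

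**Conclusion.** The point holds as a matter of safety reporting. After screening, scheduled thyroid testing follows atezolizumab, and the adverse-event definition turns what those tests find into events. Part of any thyroid difference between arms or periods would therefore come from the schedule. The direction rests on two conditions: some new asymptomatic abnormality occurs on carboplatin, and prompted tests in controls do not find all of it.

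The size, p(1 − s), cannot be derived from the documents. The range of 0.5 to 10 points illustrates assumed values and should not be cited as an estimate of bias. Nor do the documents support the inference that a thyroid excess on atezolizumab would be wholly an artefact, since they list hypothyroidism as a known risk of the drug. The primary PFS analysis is unaffected. The matter is minor and cheap to settle before the tables are made.

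**What to change.** Add to Section 17.4:

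1. Report thyroid adverse events and thyroid laboratory abnormalities found at scheduled tests as rates per tested patient on atezolizumab, and draw no between-arm difference from them. Identify them by matching the onset date to the date of the scheduled draw; Section 13.4 already requires start dates, so no new field is needed. An event with symptoms that happens to be confirmed at a scheduled draw could be misclassified, so the matching rule should be written down.
2. Show clinically prompted or symptomatic thyroid events by arm descriptively, with a note that open-label prompting and early treatment after scheduled tests may still differ by arm.
3. Assign an abnormality that is new since screening and found in the pre-dose crossover Cycle 1 sample to the carboplatin phase, not to crossover atezolizumab. It should not be labelled pre-existing: Section 13.5.4 keeps that term for conditions present at study start, and the label would hide the only scheduled thyroid evidence from the carboplatin phase.

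The cost is a few sentences and one table split, with no added tests and no change to the calendars. The trial gives up a between-arm estimate for asymptomatic thyroid events, which this testing schedule cannot support.
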